6.4 STUDY VISITS

Definitions of relevant time periods are detailed below.

Study period: January 1, 2013 – December 31, 2022

Baseline period: All available data prior to index date

Cohort identification period: January 1, 2013 – December 31, 2021 (one year before end of study period)

[figure not shown]
Statistical and Epidemiological Analysis Plan (SEAP) for Observational and Non-Interventional Studies (ONIS)

Index date: The index date for Cohort 1 will set to the date of initiation of 1L treatment; the index date for Cohort 2 will be the date of initial DDLPS diagnosis during cohort identification period.

Follow-up period: From index date until date of death, if available, or the date of censoring if there is no record of death, whichever occurs first. For survival and treatment patterns, the date of censoring will be the last activity date, defined as the date of the last visit of any type prior to the end of the study period.

Figure 1 illustrates the time periods for the study timelines.

(a). Cohort 1

(b). Cohort 2

[figure not shown]

Figure 1. Overall study period

Abbreviations: 1L = first line

7. VARIABLES

The analysis will be descriptive only, and there are no *a priori* hypotheses. There will be no prespecified exposures or covariates to be used as the basis for formal statistical testing and for *a priori* comparison of groups.

Statistical and Epidemiological Analysis Plan (SEAP) for Observational and Non-Interventional Studies (ONIS)

Page 7 of 36

7.1 OUTCOMES

7.1.1 Primary outcomes

OS

Outcome type: PrimaryOutcome name: OS

• Time frame: Time from index date until the earliest record of death or end of the study

period

■ **Population:** Cohort 1

OS as an event for each patient in Cohort 1 will be defined as the date of death minus the index date or the start day of each line of therapy (LOT). For patients with no record of death, OS will be censored at the last activity date before the end of the study period.

7.1.2 Secondary outcomes

Survival after initial diagnosis

Outcome type: Secondary

• Outcome name: Survival after initial diagnosis

• **Time frame**: Time from initial diagnosis until the earliest record of death or end of the study period

• **Population**: Cohort 1, Cohort 2

Survival after initial diagnosis for each patient will be defined as the date of death minus the date of initial diagnosis. For patients with no record of death, survival after initial diagnosis will be censored at the last activity date before the end of the study period.

Description of treatment patterns

Outcome type: Secondary

• Outcome name: Treatment patterns

• Time frame: Treatment patterns are assessed at the index date and during follow-up

■ **Population**: Cohort 1, Cohort 2

The following variables of interest will be assessed to describe treatment patterns defined by LOT and regimens.

Treatment patterns by LOT and regimens

Variable	Definition	Timing
1L Treatment Type	Regimen name from LOT data for treatments with line number = 1, 2 and 3. Treatment	Any time after
2L Treatment Type	types will be classified as follows, specific treatments and categories may change upon examination of the data:	index date
3L Treatment Type		

Statistical and Epidemiological Analysis Plan (SEAP) for Observational and Non-Interventional Studies (ONIS)

[figure not shown]
Variable	Definition	Timing
	NCCN/CSCO preferred	
	 Doxorubicin 	
	 Epirubicin 	
	 Liposomal doxorubicin 	
	AD (doxorubicin, dacarbazine)	
	 AIM (doxorubicin, ifosfamide, mesna) 	
	Ifosfamide, epirubicin, mesna	
	 Larotrectinib (NTRK fusion pos sarcomas only) 	
	 Entrectinib (NTRK fusion pos sarcomas only) 	
	 Pazopanib 	
	• Eribulin	
	Trabectedin	
	Other	
	 AD LMS only (doxorubicin, dacarbazine) 	
	Gemcitabine and docetaxel	
	Gemcitabine	
	Gemcitabine and vinorelbine	
	Gemcitabine and dacarbazine	
	 Dacarbazine 	
	 Ifosfamide 	
	Temozolomide	
	Vinorelbine	
	 Regorafenib 	
	 MAID (mesna, doxorubicin, ifosfamide, dacarbazine) 	
	 Pembrolizumab 	
	 durvalumab 	
	• Other	
Total number of treatment lines	From LOT data, for all lines after index date, categorical variable defined as total of treatment lines reported.	Any time after index date
Concurrent steroid therapy	Any record of a drug classified as a corticosteroid.	Anytime from the start to end of 1L, 2L, or 3L

Statistical and Epidemiological Analysis Plan (SEAP) for Observational and Non-Interventional Studies (ONIS)

Page 9 of 36

Variable	Definition	Timing
Concurrent	Any record of a drug classified as an	Anytime from the
immunosuppressant	immunosuppressant therapy.	start to end of 1L,
therapy		2L, or 3L
Concurrent	Any record of a drug classified as a hormone	Anytime from the
hormone	replacement therapy.	start to end of 1L,
replacement therapy		2L, or 3L

[figure not shown]
Abbreviations: 1L = first line; 2L = second line; 3L = third line; CSCO = Chinese Society of Clinical Oncology; LOT = line of therapy; NCCN = National Comprehensive Cancer Network

Property of Boehringer Ingelheim Group of Companies - Use current version only and according to confidentiality principles

[figure not shown]
Statistical and Epidemiological Analysis Plan (SEAP) for Observational and Non-Interventional Studies (ONIS)

Page 10 of 36

[figure not shown]
Statistical and Epidemiological Analysis Plan (SEAP) for Observational and Non-Interventional Studies (ONIS)

Page 11 of 36

[figure not shown]
Statistical and Epidemiological Analysis Plan (SEAP) for Observational and Non-Interventional Studies (ONIS)

Page 12 of 36

[figure not shown]
Statistical and Epidemiological Analysis Plan (SEAP) for Observational and Non-Interventional Studies (ONIS)

Page 13 of 36

Statistical and Epidemiological Analysis Plan (SEAP) for Observational and Non-Interventional Studies (ONIS)

Page 14 of 36

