9.3.1.2. Secondary outcomes

Survival after initial diagnosis

Outcome type: Secondary

• Outcome name: Survival after initial diagnosis

• **Time frame**: Time from initial diagnosis until the earliest record of death or end of the study period

• **Population**: Cohort 1, Cohort 2

NIS Protocol BI Study Number 1403-0024

Page 15 of 37 C42272174

Proprietary confidential information© 2023 Boehringer Ingelheim GmbH or one or more of its affiliated companies

Survival after initial diagnosis for each patient will be defined as the date of death minus the date of initial diagnosis. For patients with no record of death, survival after initial diagnosis will be censored at the last activity date before the end of the study period.

Description of treatment patterns

Outcome type: Secondary

• Outcome name: Treatment patterns

• Time frame: Treatment patterns are assessed at the index date and during follow-up

■ **Population**: Cohort 1, Cohort 2

The following variables of interest will be assessed to describe treatment patterns defined by LOT and regimens.

Treatment patterns by LOT and regimens

Variable	Definition	Timing
1L Treatment Type	Regimen name from LOT data for treatments with line number = 1, 2 and 3. Treatment types will be classified as follows, specific	
2L Treatment Type	treatments and categories may change upon examination of the data:	
	NCCN/CSCO preferred	
	 Doxorubicin 	
	Epirubicin	
	Liposomal doxorubicin	
	AD (doxorubicin, dacarbazine)	
	 AIM (doxorubicin, ifosfamide, mesna) 	Any time after index date
	Ifosfamide, epirubicin, mesna	
3L Treatment Type	 Larotrectinib (NTRK fusion pos sarcomas only) 	
	 Entrectinib (NTRK fusion pos sarcomas only) 	
	 Pazopanib 	
	Eribulin	
	Trabectedin	
	Other	
	AD LMS only (doxorubicin, dacarbazine)	
	Gemcitabine and docetaxel	

NIS Protocol BI Study Number 1403-0024 Page 16 of 37 C42272174

Proprietary confidential information© 2023 Boehringer Ingelheim GmbH or one or more of its affiliated companies

Variable	Definition	Timing
	Gemcitabine	
	Gemcitabine and vinorelbine	
	Gemcitabine and dacarbazine	
	Dacarbazine	
	• Ifosfamide	
	Temozolomide	
	 Vinorelbine 	
	Regorafenib	
	 MAID (mesna, doxorubicin, ifosfamide, dacarbazine) 	
	 Pembrolizumab 	
	 durvalumab 	
	• Other	
Total number of treatment lines	From LOT data, for all lines after index date, categorical variable defined as total of treatment lines reported.	Any time after index date

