6.2 SETTING

In this study, patient data from NATDSS network from January 1, 2013 to December 31, 2022 will be used. Details of data source are described in section 8.

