6.3 STUDY POPULATION

Inclusion criteria:

- Patient has two or more documented clinical visits in the National Anti-Tumor Drug Surveillance System (NATDSS) network on or after January 1, 2013.
- Patient has a confirmed diagnosis of DDLPS during his/her lifetime.
- At least 18 years old at the date of initial diagnosis

No exclusion criteria are applied.

Eligible population will be divided into two groups:

- Cohort 1 will include unresectable locally advanced or metastatic DDLPS patients who received at least one line of systemic antineoplastic treatment by the end of cohort identification period (index date = start date of first line (1L) treatment).
- Cohort 2 will include patients with DDLPS who have not initiated 1L systemic antineoplastic treatment by the end of cohort identification period (index date = date of initial DDLPS diagnosis during cohort identification period). Patients initiated 1L treatment afterwards or patients received adjuvant and/or neoadjuvant therapy only through follow-up will be included in Cohort 2.

In both cohorts, 1L therapy will be defined as the initial set of drugs used after unresectable locally advanced or metastatic diagnosis. Metastatic patients will be defined as those with metastatic diagnosis or presence of metastatic sites; unresectable locally advanced patients will be defined as those with advanced diagnosis and without subsequent surgical resection.

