10.1.2 Analysis of secondary objectives

Survival after initial diagnosis will be estimated by the KM method to obtain median estimates with 95% CIs and IORs for Cohort 1 and Cohort 2.

Treatment patterns for Cohort 1 and Cohort 2 will be described by the number of lines, count with percentage (%) of patients by treatment lines, type of therapy and therapy regimens in each line.

LOTs are defined by the temporal relationship and sequencing of treatment regimens by using the dates of initiation and discontinuation of chemotherapy, targeted therapy, and/or immunotherapy. For each patient, 1L treatment regimen is defined as the first systemic treatment of any chemotherapy, and/or targeted drugs given to a patient after advanced or metastatic DDLPS diagnosis. A treatment line is advanced to the next line when a patient initiates new combinations of drugs or has the evidence of progression of disease. The start date of each LOT is defined as the date of initiation of new regimen, and the end date of each LOT is defined as the date of last dose prescribed or recorded at/before discontinuation.

Statistical and Epidemiological Analysis Plan (SEAP) for Observational and Non-Interventional Studies (ONIS)

Page 18 of 36

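### Survival after initial diagnosis is counted from a date before patients can enter the cohort, with no delayed entry, so the Cohort 1 secondary curve is biased upward

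*SAP*

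**What the plan says.** **Who enters.** SAP 6.3 and Protocol 9.2.2 ask for a diagnosis at any time: "Patient has a confirmed diagnosis of DDLPS during his/her lifetime". They also ask for visits inside the data window: "Patient has two or more documented clinical visits in the National Anti-Tumor Drug Surveillance System (NATDSS) network on or after January 1, 2013". Cohort 1 is further limited to patients "who received at least one line of systemic antineoplastic treatment by the end of cohort identification period". Cohort 2 takes those who have not started 1L by then and is indexed at an initial diagnosis within the identification period, 1 January 2013 to 31 December 2021.

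**Which data.** SAP 6.2: "patient data from NATDSS network from January 1, 2013 to December 31, 2022 will be used".

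**Where the clock starts.** SAP 7.1.2 gives the time frame: "Time from initial diagnosis until the earliest record of death or end of the study period". Protocol 9.3.1.2: "Survival after initial diagnosis for each patient will be defined as the date of death minus the date of initial diagnosis". This applies to both cohorts.

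**How it is estimated.** SAP 10.1.2, like Protocol 9.7.2: "Survival after initial diagnosis will be estimated by the KM method to obtain median estimates with 95% CIs". The visible text has no entry time, left-truncation rule or conditional interpretation. SAP Annex 2 Table 4 and Figure 2 report the result for both cohorts.

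**What the table shells expect.** Table 2 in SAP Annex 2 has a row for initial diagnoses before 2013. Table 1 lists index years 2013 to 2021 only.

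**The concern.** Kaplan-Meier from diagnosis is valid if a patient who dies at any time after diagnosis would have been counted. Here that fails. A patient diagnosed with advanced disease who dies before systemic treatment is never in Cohort 1. One who lives to start 1L is in Cohort 1, with the whole interval from diagnosis credited as time at risk. Deaths are removed from the early part of the curve while the denominators are kept, so the estimate can only move upward. Diagnosis before 2013 adds to the problem, because such a patient must also survive to 2013.

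Protocol 9.9 names incomplete death capture as the reason survival may be overestimated and does not mention this second mechanism. Neither sensitivity analysis in Protocol 9.7.5 addresses it: one restricts by mortality coverage, and the other keeps the 2013 start. The results are meant to support a New Drug Application (Protocol 7) and may supplement regulatory submissions (Protocol 12), so an inflated natural-history benchmark could be carried forward.

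**Working it through.** **The plan's own figure.** The only survival figures are the confidence intervals for median OS from 1L in Protocol 9.5. They reproduce: simulating exponential survival with uniform entry over 120 months, administrative censoring and log-log limits gives every limit within 0.4% of the printed value. That table is sound, but it concerns OS from 1L. Nothing in the documents gives survival from diagnosis, the diagnosis-to-1L interval or the share diagnosed before 2013, so the sizes below rest on assumptions.

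**Assumptions.** Survival X from diagnosis is exponential with true median M (24 or 36 months). Time W from diagnosis to 1L is exponential with mean w (3, 6 or 12 months). The death hazard is the same before and after 1L. Diagnoses are uniform, reaching back 10 years before 2013. 1L starts in 2013 to 2021 and data end on 31 December 2022.

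**Closed form.** Let λ = ln 2 / M and μ = 1/w. Cohort 1 contains only patients with W < X. The curve that ordinary Kaplan-Meier then estimates is

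S*(t) = [(λ + μ)·exp(−λt) − λ·exp(−(λ + μ)t)] / μ.

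The second term is small near the median. Dropping it gives

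apparent median ≈ M + ln(1 + λw)/λ.

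- M = 24, w = 3: λ = 0.02888, λw = 0.0866, so 24 + 0.0831/0.02888 = 26.9.
- M = 24, w = 12: λw = 0.3466, so 24 + 0.2976/0.02888 = 34.3; keeping the second term, 33.8.
- M = 36, w = 3: λ = 0.01925, λw = 0.0578, so 36 + 0.0561/0.01925 = 38.9.
- M = 36, w = 12: λw = 0.2310, so 36 + 0.2079/0.01925 = 46.8; keeping the second term, 46.6.

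**Simulation of Cohort 1** (medians in months):

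| True median | Mean time to 1L | Diagnosed before 2013 | As planned | Diagnoses from 2013 only | Entry at 1L start |
|---|---|---|---|---|---|
| 24 | 3 | 2.6% | 27.0 | 26.9 | 24.0 |
| 24 | 6 | 4.7% | 29.6 | 29.3 | 24.1 |
| 24 | 12 | 8.3% | 33.8 | 32.9 | 24.2 |
| 36 | 3 | 2.7% | 39.0 | 38.9 | 36.0 |
| 36 | 6 | 4.9% | 41.8 | 41.5 | 36.3 |
| 36 | 12 | 9.0% | 46.8 | 45.6 | 36.4 |

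The planned estimate is high by 12.5% to 41% (27.0/24 and 33.8/24) and by 8% to 30% (39.0/36 and 46.8/36). Separate runs in which patients diagnosed before 2013 join the risk set only when 2013 begins give 26.8 to 33.5 (true 24) and 38.9 to 46.3 (true 36). Runs differ from one another by a few tenths of a month.

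The calendar boundary is therefore the smaller part in Cohort 1. The interval from diagnosis to 1L drives the bias, and only entry at 1L start removes it.

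**The case against.** **The start of 2013 and primary OS.** The Cohort 1 sentence gives 1L an upper date limit only ("received at least one line of systemic antineoplastic treatment by the end of cohort identification period"). A reader might infer that 1L before 2013 is admitted and that primary OS is overstated too. If it were, medians of 8, 10 and 12 months would read about 8.7 to 8.8, 10.9 to 11.3 and 13.2 to 13.8. The documents do not support that reading. The identification period begins on 1 January 2013 (SAP 6.4), the protocol abstract identifies patients from that date, and Table 1 has no index year before 2013 although Table 2 has such a row for diagnosis. With 1L in 2013 to 2021 this bias is zero. A reader might also fear that a later line is taken for 1L because earlier drugs lie outside the data. The direction and size of that are unknown, and part of the variable definitions cannot be seen. What remains is a wording gap.

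**Cohort 2.** On its plain reading the index rule admits only initial diagnoses from 2013 to 2021, and a row in a shared table shell may simply be empty for one cohort. This stands. Upward bias from earlier diagnoses in Cohort 2 depends on an ambiguity and is not demonstrated.

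**Existing mitigation.** Protocol 9.7.4 lists year of initial diagnosis as a possible subgroup, which could separate out diagnoses before 2013. It is optional, and the table above shows that this separation leaves most of the Cohort 1 bias in place.

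**Importance.** The outcome is secondary and descriptive, with no planned comparison. That limits the severity but does not make the estimate right.

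**Conclusion.** The point holds for survival after initial diagnosis. In Cohort 1 the direction follows from the cohort definition: the curve is biased upward. Under the stated assumptions a true median of 24 months reads about 27 to 34 and one of 36 reads about 39 to 47. These ranges are illustrative, because the documents supply neither the true median nor the diagnosis-to-1L interval, and the two-visit rule was not modelled. In Cohort 2 the bias arises to the extent that patients first come under observation after diagnosis, chiefly if diagnoses before 2013 are admitted; it is not sized for that cohort.

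Entry at 1L start recovers the true median when the timing of 1L is unrelated to later survival, as assumed here. If patients start 1L because their disease has worsened, delayed entry will not fully recover it, and a conditional label becomes the safer description. Bias in primary OS is not shown.

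**What to change.** 1. In Protocol 9.3.1.2 and 9.7.2 and SAP 7.1.2 and 10.1.2, specify left-truncated Kaplan-Meier for survival after initial diagnosis. The clock still starts at diagnosis, but a patient joins the risk set at 1L start in Cohort 1, and at the later of diagnosis and first qualifying NATDSS visit on or after 1 January 2013 in Cohort 2. Report the number at risk over time.
2. Alternatively, keep the planned estimator and label the Cohort 1 curve, in Table 4 and Figure 2, as conditional on having survived to 1L. Do not rely on restricting to diagnoses from 2013.
3. As a clarification, state in Protocol 9.2.2 and SAP 6.3 that the Cohort 1 1L start must fall between 1 January 2013 and 31 December 2021, as Table 1 implies. Reconcile the Cohort 2 index rule with the Table 2 row for diagnoses before 2013.
4. Add this mechanism to the limitations in Protocol 9.9.

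The cost is wording and one entry-time variable. Risk sets will be small soon after diagnosis, so the early part of the curve may be unstable, and the secondary medians will be shorter.

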9.7.5. Sensitivity analyses

Sensitivity analyses will be conducted:

- to only include patients in areas covered by the mortality surveillance system and with higher completeness on survival data.
- to only include patients before COVID-19 emergence (cohort identification period: January 1, 2013 December 31, 2019) to assess the possible impact of COVID-19 pandemic on treatment patterns and outcomes.

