9.9. LIMITATIONS OF THE RESEARCH METHODS

There are several limitations of this study. Firstly, CDC mortality surveillance data may only capture 80% of the total deaths, which may result in over-estimate of the survival outcomes. We attempt to conduct sensitivity analyses in area with higher completeness on survival data. Still, results should be interpreted with caution.

Secondly, the study could be subjected to missing clinical information that is not routinely recorded by clinicians, variations in the reporting, and selection biases arise from the use of diagnostic and therapeutic codes. Under-reporting of comorbidities and of treatment received outside the oncology clinic setting may result in misclassification of treatments and outcomes.

Additionally, as this study population includes patients from tertiary or oncology hospitals in China, study results might not be generalizable to entire Chinese DDLPS patients. As oncology care remain only possible or most optimally delivered though face-to-face, patients' access to oncological services is possibly limited during COVID-19 pandemic impacts, consequently resulting in less patient diagnosis and hospital visits.

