8. DATA SOURCES

will develop a custom, curated dataset for this study based on longitudinal electronic medical records (EMR) data from the NATDSS, the largest cancer registry database in China. This database, established in 2018 by China National Cancer Center (NCC), covers over 1400 hospitals across 31 provinces and over 10 million cancer patients in

Statistical and Epidemiological Analysis Plan (SEAP) for Observational and Non-Interventional Studies (ONIS)

Page 15 of 36

China. This multicenter hospital-based database consists of data of 1509 variables from 7 aspects including drug, patient basic information, inpatient, outpatient, tests and examinations, treatment and follow up. NATDSS is linked with National Mortality Database from Chinese Center for Disease Control and Prevention Center (China CDC) to obtain patients' death information [R23-1183].

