10. DATA ANALYSIS

The statistical analysis plan for the study is summarized below. This study will be descriptive in nature.

For continuous variables, they'll be descriptively summarized using the mean with the standard deviation (SD), the median with the interquartile range (IQR), and the maximum and minimum values, as appropriate.

For categorical variables, the numbers and proportions of patients in different categories of the variable will be reported. Missing values will be presented as counts and percentages but excluded from the denominator when calculating proportions, unless there are additional instructions specified.

For time-to-event variables, the number and percentage of patients with events and censoring

Statistical and Epidemiological Analysis Plan (SEAP) for Observational and Non-Interventional Studies (ONIS)

Page 17 of 36

will be summarized. The median survival time and its 95% confidence interval (CI) will be calculated using the Kaplan–Meier (KM) method, and KM plots will be provided.

It is anticipated that sample sizes for variables may vary due to unknown or missing data in the database. The number of patients with missing data for each variable will be summarized and reported. With the exception of the imputation of partial missing date values, no other imputation of missing values will be undertaken; however, the impact of missing data on interpretation of findings will be acknowledged and discussed in the final study report.

For all analyses, data for patients will be censored when lost to follow-up (i.e., still alive as of their last visit prior to end of study period).

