ANNEX 2. MOCK TABLE AND FIGURE

The following figures and tables will be developed for analyses of primary, secondary and exploratory objectives and will be replicated for subgroup analyses and sensitivity analyses, pending feasibility.

Table 1. Patient baseline demographic characteristics for Cohort 1 and Cohort 2

Demographic characteristics	Cohort 1	Cohort 2
Number of patients, N		
Index year, N (%) 2013		
2014		
2015		
2016		
2017		
2018		
2019		
2020		
2021		
Age at initial diagnosis, years		
$Mean \pm SD$		
Median (IQR)		
Min, Max		
Missing / Unknown		
Age (categorized) at initial diagnosis, N (%)		
<65		
≥65		
Missing / Unknown		
Age at index, years		
$Mean \pm SD$		
Median (IQR)		
Min, Max		

Statistical and Epidemiological Analysis Plan (SEAP) for Observational and Non-Interventional Studies (ONIS)

Page 21 of 36

Demographic characteristics	Cohort 1	Cohort 2
Missing / Unknown		
Age (categorized) at index, N (%)		
<65		
≥65		
Missing / Unknown		
Sex, N (%)		
Female		
Male		
Missing / Unknown		
Insurance type, N (%)		
National medical insurance		
Commercial insurance		
Out of pocket		
Others		
Missing / Unknown		
Region, N (%)		
Eastern China		
Central China		
Western China		
Northeast China		
Missing / Unknown		

Abbreviations: N = number; SD = standard deviation; IQR = interquartile range; min = minimum; max = maximum

Notes: Eastern China includes Beijing, Tianjin, Hebei, Shanghai, Jiangsu, Zhejiang, Fujian, Shandong, Guangdong, and Hainan; central China includes Shanxi, Anhui, Jiangxi, Henan, Hubei, and Hunan; western China includes Inner Mongolia, Guangxi, Chongqing, Sichuan, Guizhou, Yunnan, Tibet, Shaanxi, Gansu, Qinghai, Ningxia, and Xinjiang; northeast China includes Liaoning, Jilin, and Heilongjiang.

Statistical and Epidemiological Analysis Plan (SEAP) for Observational and Non-Interventional Studies (ONIS)

Page 22 of 36

Table 2. Patient clinical characteristics for Cohort 1 and Cohort 2

Clinical characteristics	Cohort 1	Cohort 2
Number of patients, N Year of initial diagnosis, N (%)		
Before 2013		
2013		
2014		
2015		
2016		
2017		
2018		
2019		
2020		
2021		
Missing / Unknown		
Disease stage at initial diagnosis, N (%)		
0		
I		
II		
III		
IV		
Missing / Unknown		
Histology, N (%)		
Dedifferentiated		
Other		
Missing / Unknown		
ECOG performance status, N (%)		
0		
1		
2		
3		
4		
Missing / Unknown		

Statistical and Epidemiological Analysis Plan (SEAP) for Observational and Non-Interventional Studies (ONIS)

Page 23 of 36

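### Survival after diagnosis, as most naturally read, counts registry deaths after the last visit but censors everyone else at that visit; the plan should settle the rule, name both opposing biases and show how far the result depends on it.

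*SAP*

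**What the plan says.** Survival after initial diagnosis is a secondary outcome for both cohorts and is reported in SAP Annex 2, Table 4.

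- **Outcome and censoring.** SAP 7.1.2 and Protocol 9.3.1.2 run the time from diagnosis to the first death record or study end. Patients "with no record of death, survival after initial diagnosis will be censored at the last activity date before the end of the study period". SAP 6.4 gives last activity as "defined as the date of the last visit of any type prior to the end of the study period". It ends follow-up at the date of death where there is one and uses the censoring date only where there is none.
- **Source of deaths.** SAP 8: "NATDSS is linked with National Mortality Database from Chinese Center for Disease Control and Prevention Center". SAP 10.1.1 names that database as the source of the death date for OS; SAP 7.1.2 names no source. The data cover "7 aspects including drug, patient basic information, inpatient, outpatient, tests and examinations, treatment and follow up".
- **Wording that points another way.** The protocol abstract follows patients to death, study end or loss to follow-up, whichever is first. SAP 10, like Protocol 9.7, says: "For all analyses, data for patients will be censored when lost to follow-up (i.e., still alive as of their last visit" before study end.
- **Biases and sensitivity analyses.** Protocol 9.9: "CDC mortality surveillance data may only capture 80% of the total deaths, which may result in over-estimate of the survival outcomes". Protocol 9.7.5 plans one analysis "to only include patients in areas covered by the mortality surveillance system and with higher completeness on survival data" and one restricted to the period before COVID-19. SAP Annex 2 says that its tables "will be replicated for subgroup analyses and sensitivity analyses, pending feasibility".

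The SAP text between 10.1.2 and 10.3 is not in the public version, so the sensitivity analyses are judged from Protocol 9.7.5.

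**The concern.** Take two patients who both stop attending in 2016. One dies in 2020 and the registry records it: an event in 2020, with the patient in the risk set until then. The other is alive at the end of 2022 and is censored in 2016. Their visit histories are the same, and only the later outcome decides who stays in the risk set. Kaplan-Meier needs censoring to be unrelated to the outcome.

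At stake are the medians and the 6- to 24-month rates in Table 4. Cohort 2 includes patients who had only adjuvant or neoadjuvant therapy. They may live longer and attend less, and if so the rule matters most there. Restricting to high-completeness areas reduces the bias from missed deaths but leaves this one in place and unnamed, so that analysis could be taken for the corrected answer.

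**Working it through.** **1. The plan's own figure.** The only numerical planning figure is the OS precision table in Protocol 9.5. With exponential survival, uniform entry, a window set to give 20% censoring, and log-log intervals, all 12 cells reproduce within 0.8% (N = 300, median 8: 6.73 to 9.46 against 6.732 to 9.435). That table assumes censoring unrelated to outcome. There is no planning figure for survival after diagnosis.

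**2. Direction.** Kaplan-Meier is the product of (1 − d/n) over the death times. Under last-activity and study-end censoring the recorded deaths d are the same. Earlier censoring of the others can only reduce n. Every factor is therefore equal or smaller, and the planned curve can never lie above the study-end curve.

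**3. Size at full capture.** From the documents: entry 2013-2021 and study end 31 December 2022, so potential follow-up A is taken as uniform on 12-120 months. Assumed, because the documents give no values: exponential survival with rate λ = ln 2 / median; a share p in contact to death or study end; visits stopping at an exponential time with mean μ for the rest. With S(t) = e^(−λt), G(t) = (120 − max(12, t))/108, and E(t) = (1/108) × the integral of e^(−λa) for a from max(12, t) to 120, the hazard that Kaplan-Meier sees is

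λ × S·G / [S·G − (1 − p)(1 − e^(−t/μ))·E].

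Example: true median 36, μ = 24, p = 0, t = 24.
- λ = 0.693/36 = 0.01925, S = 0.630, G = 96/108 = 0.889, so S·G = 0.560.
- E = 0.255 and 1 − e^(−1) = 0.632, so survivors already removed are 0.632 × 0.255 = 0.161.
- The hazard is inflated by 0.560/(0.560 − 0.161) = 1.40.

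The median is where the accumulated hazard reaches ln 2:

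| True median | Visits stop for all (μ = 12 / 24 / 60) | Visits stop for half | Visits stop for none |
|---|---|---|---|
| 36 | 26.2 / 29.0 / 32.2 | 30.8 / 32.3 / 34.1 | 36 |
| 60 | 33.9 / 39.6 / 47.6 | 45.8 / 48.8 / 53.3 | 60 |

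Simulation with 400,000 patients per scenario agrees. Visits on a 3-month grid lower these by about half a month (true 36) to one month (true 60). If instead survivors' last visit falls 3, 6, 12 or 24 months before study end, true 36 becomes 35.2, 34.4, 32.8 or 29.9.

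**4. Planned rule at 80% capture** (the figure in Protocol 9.9), simulated over both visit patterns:

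| True median | Stop for all | Stop for half | Stop for none |
|---|---|---|---|
| 36 | 28-38 | 35-41 | 44-45 |
| 60 | 35-55 | 53-64 | 73-75 |

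The net error can have either sign.

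**5. Study-end censoring at capture c.** The curve estimates 1 − c(1 − S), so the apparent median is the true median × [−ln(1 − 0.5/c)]/ln 2. For c = 0.80: −ln(0.375) = 0.981, and 0.981/0.693 = 1.415.

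| Capture | Factor | True 36 | True 60 |
|---|---|---|---|
| 100% | 1.000 | 36 | 60 |
| 95% | 1.078 | 39 | 65 |
| 90% | 1.170 | 42 | 70 |
| 85% | 1.280 | 46 | 77 |
| 80% | 1.415 | 51 | 85 |

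**6. The two rules are not bounds.** For true 36, all in contact and 95% capture, last-activity censoring gives 37.4-37.8 and study-end censoring 39: both are too high.

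**7. Primary OS, full capture.** True 8, 10 and 12 give 7.8-8.0, 9.6-10.0 and 11.4-12.0. The largest shift is (12 − 11.4)/12 = 5%.

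**The case against.** **The asymmetry is inferred.** The abstract and the general censoring sentence can be read as ending follow-up at loss even if a death is recorded later, and then it does not arise. This stands as a reason to reconcile the text. SAP 6.4 and 7.1.2 are the specific definitions, and they point to counting the later death.

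**The large figures rest on undocumented inputs.** The medians of 36 and 60 months and all stopping rates are assumed. Taking 60 down to about 34 needs survivors to be out of contact for a mean of 44 months. The documents' only survival figures are 8-12 months from first-line treatment, where the effect is small. The model also ignores cohort selection: Cohort 1 must survive to first-line treatment and may include diagnoses before 2013, and Cohort 2 is defined by not starting it by the end of 2021. All of this stands, so the sizes are illustrative.

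**Visits of any type, and follow-up data, may keep last activity close to study end.** This also stands. The bias would then be small, and reporting the gap would show it.

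**A study-end run says little.** At 80% capture it is much further off than the planned rule with half in contact (51 against 35-41, for a true 36). The difference between the rules is also ambiguous. At n = 300 it averages 3.7 months with half in contact (μ = 24) and full capture, and 2.1 months with all in contact and 90% capture. That limits the run to a subset where capture is documented to be high.

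**Stronger readings.** A reader might infer that Table 4 will underestimate survival, that the two rules bracket the truth, or that primary OS is seriously biased. The documents support none of these: capture may be only 80%, contact is unknown, both rules can exceed the truth, and OS medians of 8-12 months move at most 5%.

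**Conclusion.** The point holds in a limited form. On the most natural reading, the rule makes censoring depend on the outcome and can only lower the curve relative to study-end censoring. That direction needs no distributional assumption. The size does: it runs from nothing, where contact continues to the end, to roughly a quarter of a 36-month median, where all patients stop visiting after a mean of 12 months and capture is full (36 to 26.2, or −27%). Against true survival the net sign is unknown, because missed deaths push the other way and neither contact nor capture is known for these cohorts. The visible plan names one direction only and gives the reader no means of judging the other. It does not follow that the main censoring rule is wrong or that the primary analysis needs to change.

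**What to change.** 1. Reconcile the protocol abstract, Protocol 9.7 and SAP 10 with SAP 6.4 and 7.1.2 on whether a death recorded after the last visit counts. Name the death source for survival after diagnosis, and state whether follow-up contacts count as last activity.
2. Report the distribution of time from last activity to 31 December 2022 in patients without a death record, by cohort.
3. In the high-completeness sensitivity analysis, where replication of Table 4 is subject to feasibility, add a column that censors patients without a death record at 31 December 2022, or at the registry linkage cut-off if earlier, with that date given. State the death capture in that subset and label the column as biased upward when capture is below 100%. Present the difference as dependence on the censoring rule, not as bounds.
4. Add to the limitations that two opposing biases exist, missed deaths and outcome-dependent censoring, with unknown net sign.

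Keep last-activity censoring as the main rule and for OS.

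The cost is a few sentences, one descriptive line and one table column. The downside is that the added column overshoots as capture falls (step 5), so it informs only where capture is documented to be high.
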